After completion of treatment for 6 months (Week 25) and data collection for the primary analysis, the patients will continue on long-term avalglucosidase alfa treatment and follow-up in the Extension Period for up to a total of 3 years in the study. Cohort 3 patients receiving alglucosidase alfa will have the option to switch to treatment with avalglucosidase alfa maximum tolerated dose (MTD) as determined based on safety data from both dose levels in Cohort 1 and Cohort 2 in the extension period or discontinue the study. The data cut-off for the primary

analysis will be after the last patient in Cohort 3 has completed 6 months of treatment (Week 25) and analysis will be conducted on all data available by then.

Safety, efficacy, PK and [REDACTED] will be performed at scheduled visits throughout the study treatment period. Ventilator use, adverse events (AEs) and concomitant and pre-infusion medications/therapies will be monitored continuously throughout the study.

If a patient in Cohort 1, receiving 20 mg/kg qow avalglucosidase alfa, experiences further clinical decline at or after Week 25 when compared to prior to enrollment in ACT14132, and as defined by more rapid worsening of criteria of clinical decline, which is sustained on repeated study assessments, the patient may be managed per the discretion of the Investigator, which may include return to treatment with commercially available alglucosidase alfa (and termination of study participation) or increasing the avalglucosidase alfa dose to 40 mg/kg qow or MTD, once established, while being enrolled in the extension period of the study.

If a patient in Cohort 2 or 3 experiences further clinical decline at or after Week 25 as defined by more rapid worsening of criteria of clinical decline than prior to study start, which is sustained on repeated study assessments, the patient may be managed per the discretion of the Investigator. This may include return to treatment with commercially available alglucosidase alfa (and termination of study participation).

Patients must have completed the 25-week treatment period of the study before dose increase of avalglucosidase alfa (or start of avalglucosidase alfa for patients receiving alglucosidase alfa in Cohort 3) will be considered.

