2.2 DISPOSITION OF PATIENTS

This section describes patient disposition for both patient study status and the patient analysis populations.

Screened patients will be defined as any patient who has signed the informed consent form.

Randomized patients consist of all Cohort 3 patients who have had a treatment kit number allocated and recorded in the interactive response technology (IRT) database, regardless of whether the treatment kit was used.

For cohort 3, patients treated without being randomized, if any, will not be considered as randomized and will not be included in any efficacy population.

For patient study status, the total number of patients in each of the following categories will be presented using a summary table:

- Screened patients,
- Screen failure patients and reasons for screen failure (if data is available),
- Treated patients (Stage 1),
- Randomized patients (Stage 2),
- Nonrandomized but treated patients (Stage 2),
- Randomized and treated patients (Stage 2),
- Randomized but not treated patients (Stage 2),
- Number and percentage of patients who completed the treatment epoch for PAP,
- Number and percentage of patients who did not complete the treatment epoch for PAP, with corresponding reasons.
- Patients who continued into ETP,
- Patients who completed ETP,
- Number and percentage of patients who did not complete the ETP treatment, with corresponding reasons,
- Number and percentage of patients who did not complete the ETP follow-up, with corresponding reasons (will be included in final study report only).
- Number and percentage of patients who received increased or decrease dose, i.e. increase from 20 mg/kg qow to 40 mg/kg qow (Cohort 1), or decrease from 40 mg/kg qow to 20 mg/kg qow.

For all categories of patients (except for the screened and randomized/nonrandomized categories), the summaries will be provided by study cohort and randomized treatment, and percentages will be calculated using the number of safety patients (Stage 1) or randomized patients (Stage 2) as the denominator.

A listing of patients who received increased or decrease dose will also be provided.

All critical or major deviations potentially impacting efficacy analyses, randomization (Cohort 3), and drug-dispensing irregularities, and other major or critical deviations will be listed by patient for all enrolled patients and also summarized in tables giving numbers and percentages of deviations by study cohort and randomized treatment.

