2.3 ANALYSIS POPULATIONS

2.3.1 Safety population

The safety population is the primary population for Stage 1 and the overall study safety analysis.

The safety population will include patients who receive at least 1 infusion (partial or total). The safety population will be analyzed according to treatment received. For PAP, safety population includes patients who receive at least 1 infusion in PAP. For ETP, safety population includes patients who receive at least 1 infusion in ETP. Overall safety of alglucosidase alfa will be based on patients who receive at least 1 infusion during either PAP or ETP.

For Cohort 1 and Cohort 2, patients for whom it is unclear whether IMP was administered will be included in the safety population. For cohort 3, randomized patients for whom it is unclear whether they took the IMP will be included in the safety population as randomized.

For Cohort 3, nonrandomized but treated patients, if any, will not be part of the safety population in PAP; however, their safety data will be presented separately in PAP.

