2.4.3 Extent of investigational medicinal product exposure and compliance

2.4.3.1 Extent of investigational medicinal product exposure

The extent of study drug exposure will be assessed by the duration of study drug exposure (weeks), number of infusions, amount of dose received and total duration of study drug exposure (patient \times years). The extent of study drug exposure will be summarized in the safety population.

Duration of study drug exposure is defined below:

For PAP,

- Duration of IMP exposure is defined as the first dose date in ETP (or 14 days after the last dose date in PAP if the patient is not continuing in ETP) minus (–) the first dose date in PAP, regardless of unplanned intermittent discontinuations.

For ETP,

- Duration of IMP exposure is defined as 14 days after last dose in ETP minus (–) the first dose date in ETP, regardless of unplanned intermittent discontinuations.

For the overall treatment duration,

- Duration of avalglucosidase alfa total exposure is defined as 14 days after last avalglucosidase alfa dose in study minus (–) first avalglucosidase alfa dose date in the study. This is defined for all patients other than the Cohort 3 alglucosidase alfa patients.

The duration of IMP exposure will be summarized descriptively as a continuous variable, as well as a categorical variable (e.g., <12 weeks, 12 to <24 weeks, \geq 24 weeks for PAP).

The cumulative dose information for the considered period (PAP, ETP, or the overall treatment period) will be assessed by the total number of infusions received in the considered period, as well as total amount of IMP in mL (if this information is available from the database) received in the considered period. These data will be summarized descriptively.

For Cohorts 1 and 2, and Cohort 3 avalglucosidase alfa patients, both duration of IMP exposure and cumulative dose will be summarized for PAP, ETP, as well as the overall treatment period.

For Cohort 3 alglucosidase alfa patients, both duration of IMP exposure and cumulative dose will be summarized for PAP; in addition, duration of IMP exposure will be summarized for ETP after switching to avalglucosidase alfa.

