2.4.4 Analyses of safety data

In general, for PAP, the summary of safety results will be presented by study cohort and treatment arm. For the overall avalglucosidase alfa treatment period, the summary of safety results will be presented by initial planned dose levels among avalglucosidase alfa patients. For Cohort 3 alglucosidase alfa patients, the summary of safety results for ETP will be presented in separate tables.

In the PAP analysis, the safety analyses will be carried out with patients by the actual treatment received, irrespective of the treatment the patient has been randomized to. The actual treatment received is defined as:

- avalglucosidase alfa if the patient receives at least one infusion with this drug in PAP;
- alglucosidase alfa if the patient only receives alglucosidase alfa in PAP.

In the ETP analysis and/or overall evaluation of avalglucosidase alfa safety, the safety analyses will be carried out by the following 3 groups:

- AVAL/AVAL in ETP includes data in ETP among patients who received avalglucosidase alfa in PAP and ETP;
- ALGLU/AVAL in ETP includes data in ETP among patients who received alglucosidase alfa in PAP and received avalglucosidase alfa in ETP;
- AVAL/AVAL and ALGLU/AVAL in overall avalglucosidase alfa treatment period includes data in PAP and/or ETP among patients who received avalglucosidase alfa in that period.

General rules

All safety analyses will be performed on the safety population as defined in [Section 2.3.1](#), unless otherwise specified, using the following common rules:

- The safety baseline value is defined the same as the baseline definition in [Section 2.1.1](#).
- The potentially clinically significant abnormality (PCSA) values are defined as abnormal values considered medically important by the Sponsor according to predefined criteria/thresholds based on literature review and defined by the Sponsor for clinical laboratory tests, vital signs, and ECG (PCSA version dated January 2014 [[Appendix B](#)]).
 - PCSA criteria will determine which patients had at least 1 PCSA during the treatment epoch (for PAP and ETP respectively), taking into account all evaluations performed during this period, including nonscheduled or repeated evaluations.
 - The number of all such patients will be the numerator for the on-treatment PCSA percentage; the denominator will be the number of patients assessed for that given parameter in the treatment epoch by treatment group on the safety population.

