- For the overall evaluation of avalglucosidase alfa safety, selected analysis will be repeated by dose levels among avalglucosidase alfa patients
- The analysis of the safety variables will be essentially descriptive and no inferential testing is planned.

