- All TEAEs during PAP presented by PT, sorted by decreasing incidence of PT in the avalglucosidase alfa arm.

- All TEAEs regardless of relationship and related to IMP during PAP by primary SOC, and PT.
- All TEAEs during PAP by maximal severity (i.e., mild, moderate, or severe), presented by primary SOC and PT.
- Most common TEAEs during PAP by primary SOC and PT sorted by the internationally agreed SOC order and by decreasing incidence of PTs within each SOC. The most common TEAE are defined as those preferred terms occurring in ≥ 2 patients.
- Listing of TEAEs.

Analysis of treatment-emergent SAE(s) in PAP

- All treatment-emergent SAEs during PAP, by primary SOC and PT.
- All treatment-emergent SAEs regardless of relationship and related to IMP during PAP, by primary SOC and PT.
- Listing of treatment-emergent SAEs.

Analysis of TEAE(s) leading to treatment discontinuation in PAP

- TEAEs leading to permanent treatment discontinuation during PAP, by primary SOC and PT.
- TEAEs leading to permanent treatment discontinuation during PAP presented by PT, sorted by decreasing incidence of PT in the avalglucosidase alfa arm.
- Listing of TEAEs leading to permanent treatment discontinuation during PAP, including details on dose, severity, and relationship, etc.

Analysis of adverse events with AESIs in PAP

- Treatment-emergent AESIs during PAP, by primary SOC and PT, showing the n and % of patients, sorted by decreasing incidence of PT within the avalglucosidase alfa arm.
- Treatment-emergent protocol-defined IARs during PAP, by primary SOC and PT, presented by overall n and %, as well as by start time of IAR in relation to end of infusion time (during infusion, ≤ 2 hours, >2 to 24 hours, >24 to 72 hours, >72 hours).
- Treatment-emergent algorithm-defined IARs during PAP, by primary SOC and PT, presented by overall n and %, as well as by start time of IAR in relation to end of infusion time (during infusion, ≤ 2 hours, >2 to 24 hours, >24 to 72 hours, >72 hours).
- Treatment-emergent protocol-defined IARs during PAP, by PT and maximal severity, presented by overall n and %, as well as by start time of IAR in relation to end of infusion time (during infusion, ≤ 2 hours, >2 to 24 hours, >24 to 72 hours, >72 hours).

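### Long-term avalglucosidase alfa safety is grouped by initial planned dose, and no table is expressly defined by the dose being received after a dose change

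*SAP*

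**What the plan says.** **Grouping rule.** SAP 2.4.4 sets the main rule for the overall avalglucosidase alfa period: "the summary of safety results will be presented by initial planned dose levels among avalglucosidase alfa patients". The same section adds three groups for the extension and overall evaluation, defined by drug sequence. The widest is described as "AVAL/AVAL and ALGLU/AVAL in overall avalglucosidase alfa treatment period includes data in PAP and/or ETP among patients who received avalglucosidase alfa in that period". Dose plays no part in any of the three.

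**Treatment received.** SAP 2.3.1 states: "The safety population will be analyzed according to treatment received". SAP 2.4.4 then defines the treatment actually received by drug only, and only for the primary analysis period (PAP).

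**Dose changes.** SAP 1.1 allows a Cohort 1 patient with further sustained decline to be managed by "increasing the avalglucosidase alfa dose to 40 mg/kg qow or MTD, once established, while being enrolled in the extension period of the study". Protocol 8.1.2 says the same, on condition that the higher dose has been found acceptable. SAP 2.2 plans to count and list patients with an "increase from 20 mg/kg qow to 40 mg/kg qow (Cohort 1), or decrease from 40 mg/kg qow to 20 mg/kg qow".

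**Dose levels elsewhere.** The general rules in SAP 2.4.4 add: "For the overall evaluation of avalglucosidase alfa safety, selected analysis will be repeated by dose levels among avalglucosidase alfa patients". SAP 2.4.4.3 (laboratory), 2.4.4.6 (physical examination) and 2.4.4.7 (immunogenicity) also plan summaries by dose level. The Protocol does so in its synopsis, which names 20 and 40 mg/kg, and in 11.4.2. None of these places says whether the initial or the current dose is meant.

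**Exposure.** SAP 2.4.3.1 begins: "Duration of avalglucosidase alfa total exposure is defined as 14 days after last avalglucosidase alfa dose in study", and subtracts the first dose date. There is no split at a dose change.

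**The concern.** Safety is the primary objective, and the overall-period tables are the planned long-term view by dose. If a Cohort 1 patient is escalated, the rule in SAP 2.4.4 leaves that patient's later events and exposure under 20 mg/kg, although the infusions are at 40 mg/kg. After a decrease the misplacement runs the other way. A reader comparing the two columns would not see what happened at the dose being given.

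The two documents also differ in wording. The Protocol refers to dose levels; the SAP adds that they are the initial planned ones. Neither of the SAP's own lists of changes (1.5 and 1.6) mentions this. The SAP says it was written against a protocol version dated 27 July 2018, which is not the version reviewed here. The later amendment tables, however, report no change to the dose-level grouping in Protocol 11.4.2.

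**Working it through.** There is no figure in the plan to reproduce. The check has two parts.

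**1. Does any planned output show safety by the dose being received?**

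- *Main overall-period tables (SAP 2.4.4):* initial planned dose. No.
- *Three drug-sequence groups (SAP 2.4.4):* doses pooled. No.
- *Repeats by dose level (SAP 2.4.4 general rules, 2.4.4.3, 2.4.4.6, 2.4.4.7):* the term is not defined for a patient who changes dose. The natural reading carries over the initial-planned rule set just before it, but no cross-reference says so. Undetermined.
- *AE counts (SAP 2.4.4.1):* the same event counts once per patient within a treatment phase. An event seen in the extension at 20 mg/kg and again at 40 mg/kg therefore adds nothing to the patient count.
- *Kaplan-Meier TEAE estimates (SAP 2.4.4.1):* by 6-month interval, without a split by dose.
- *AE listings:* Protocol 11.4.2.1 names severity, relationship, action taken and outcome. The one listing said to show dose is the "Listing of TEAEs leading to permanent treatment discontinuation during PAP, including details on dose, severity, and relationship, etc", and no increase is permitted before the PAP is complete. SAP 2.4.4.1 repeats selected PAP analyses for the extension without saying which.
- *Disposition (SAP 2.2):* identifies the patients who changed dose, but gives no safety by dose.

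So no table is expressly defined by the dose being received, and no rule assigns events or exposure after a change.

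**2. How much of the 20 mg/kg column could be affected?**

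Inputs from the Protocol: 13 infusions to Week 25 (8.1.1), up to 60 from Week 27 to Week 145 (8.1.2), at least 5 patients in Cohort 1 (6.1). Assumptions: full dosing to Week 145; one escalation; 40 mg/kg found acceptable, so that Cohort 3 also receives 40 mg/kg and the 20 mg/kg column is Cohort 1 alone.

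Infusions per patient: (145 − 1)/2 + 1 = 73 = 13 + 60.

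Infusions from week w to Week 145: (145 − w)/2 + 1.

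Column total: 5 × 73 = 365; with 6 patients, 6 × 73 = 438.

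| Escalation at | Infusions at 40 mg/kg | Share of column, n = 5 | Share, n = 6 |
|---|---|---|---|
| Week 27 | 60 | 60/365 = 16.4% | 13.7% |
| Week 49 | 49 | 49/365 = 13.4% | 11.2% |
| Week 73 | 37 | 37/365 = 10.1% | 8.4% |
| Week 97 | 25 | 25/365 = 6.8% | 5.7% |

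Week 27 is possible: Protocol 10.1.2.6 schedules motor tests and echocardiography at both Week 13 and Week 25, so a sustained decline could be documented by then. The later rows follow the six-monthly assessments in Protocol 10.1.3.7.

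The 40 mg/kg side is less affected. With 10 patients started at 40 mg/kg (5 in Cohort 2 and 5 in Cohort 3), one Week 49 escalation leaves 49/(10 × 73 + 49) = 49/779 = 6.3% of all 40 mg/kg infusions outside that column. If 5 switch patients with 60 infusions each are also counted there, it is 49/(730 + 300 + 49) = 49/1079 = 4.5%.

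These are shares of infusions, not of events.

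**The case against.** Initial planned dose is a legitimate patient-level grouping: it fixes the denominators and keeps each patient in one column. In a study of about 20 patients, the few who change dose are counted and listed, so dose at onset could probably be traced by reading listings together, if these carry the dates. All safety analyses are descriptive, and the pooled group loses no event. A table by dose at onset might hold one to three patients after the change, would place them in two columns, and would be confounded because escalation follows clinical decline.

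Most of this stands. It supports keeping initial planned dose as the main display and rating the point low. It does not supply the missing attribution rule.

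A reader might go further and infer that the SAP rules out every table by received dose. The text does not support that. Four places in SAP 2.4.4 and its subsections, and two in the Protocol, refer to dose levels without the words initial planned. Tables by received dose are neither promised nor excluded; the term is undefined.

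A reader might also infer that the primary safety analysis or the dose selection is compromised. It is not, as far as escalation goes. Protocol 11.4.2.1 bases the primary AE analysis on onset within 25 weeks, and no increase is allowed before that period is complete. An increase to 40 mg/kg also waits for the DMC's review of both dose cohorts.

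**Conclusion.** The point holds in a limited form. Under the rule in SAP 2.4.4, events and exposure after a dose change stay with the starting dose. No output is expressly defined by the dose being received, and the SAP's wording is narrower than the Protocol's without being recorded as a modification.

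The size depends on facts the documents do not give. With 5 Cohort 1 patients, full dosing to Week 145 and a single escalation, about 7% to 16% of the 20 mg/kg column's infusions would be at 40 mg/kg. If nobody changes dose, the effect is nil.

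This is a minor point and a cheap improvement. It does not show that the initial-dose tables are wrong or that any result is biased in a known direction.

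**What to change.** 1. Keep initial planned dose as the main overall-period display.
2. Reconcile the rule in SAP 2.4.4 with its own general rules, with SAP 2.4.4.3, 2.4.4.6 and 2.4.4.7, and with the Protocol synopsis and 11.4.2. State for each table whether dose level means the initial planned dose or the dose received, and record the choice in SAP 1.5 or 1.6. Cumulative patient-level measures such as ADA can reasonably stay under the initial dose.
3. For overall-period TEAEs, SAEs and IARs only, add a supplementary summary by dose being received at onset, with patient-years split at the date of change.
4. Show dose at onset in the overall-period AE listings.

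The cost is SAP wording and one supplementary set of tables; dosing data are already collected. The new summary should be labelled descriptive, with a note that a patient can appear in two columns, that the post-change group may be very small, and that escalation follows decline.

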2.4.4.1 Analyses of adverse events

Generalities

The primary focus of AE reporting will be on TEAEs. Pre-treatment AEs and post-treatment AEs will be described separately.

If an AE date/time of onset (occurrence, worsening, or becoming serious) is incomplete, an imputation algorithm will be used to classify the AE as pre-treatment, treatment-emergent, or post-treatment. The algorithm for imputing date/time of onset will be conservative and will classify an AE as treatment-emergent unless there is definitive information to determine it is pre-treatment or post-treatment. Details on classification of AEs with missing or partial onset dates are provided in [Section 2.5.3](#).

AE summaries will include number (n) and percentage of patients experiencing an AE by study cohort and treatment group. Multiple occurrences of the same event in the same patient will be counted only once in the tables within a treatment phase. The denominator for computation of percentages is the number of patients in the specific population within each study cohort or treatment group. The number of different AE events will be included in some summaries as well whenever appropriate.

Unless otherwise specified, sorting order will follow the internationally agreed SOC order, and further by decreasing number of events in PTs within SOCs in the avalglucosidase alfa arm. When more than one PT has same number of events, the order of presentation will be alphabetical in PTs.

Analysis of TEAE(s) in PAP

The following TEAE summaries will be generated for the safety population.

- An overview of TEAEs in PAP, including:
 - TEAEs,
 - TEAEs potentially related to study drug,
 - Serious TEAEs,
 - Serious TEAEs potentially related to study drug,
 - Severe TEAEs,
 - Severe TEAEs potentially related to study drug
 - TEAEs leading to permanent treatment discontinuation,
 - TEAEs leading to death,
 - TEAEs leading to death potentially related to study drug
 - Protocol-defined IARs,
 - Algorithm-defined IARs.
- All TEAEs during PAP by primary SOC, HLG, HLT, and PT, showing n and % of patients with at least one TEAE sorted by the SOC internationally agreed order. The other levels (HLG, HLT, PT) will be presented in alphabetical order.
- All TEAEs during PAP by primary SOC and PT sorted by the internationally agreed SOC order and by decreasing incidence of PTs within each SOC for the avalglucosidase alfa arm.
- All TEAEs during PAP presented by PT, sorted by decreasing incidence of PT in the avalglucosidase alfa arm.

- All TEAEs regardless of relationship and related to IMP during PAP by primary SOC, and PT.
- All TEAEs during PAP by maximal severity (i.e., mild, moderate, or severe), presented by primary SOC and PT.
- Most common TEAEs during PAP by primary SOC and PT sorted by the internationally agreed SOC order and by decreasing incidence of PTs within each SOC. The most common TEAE are defined as those preferred terms occurring in ≥ 2 patients.
- Listing of TEAEs.

Analysis of treatment-emergent SAE(s) in PAP

- All treatment-emergent SAEs during PAP, by primary SOC and PT.
- All treatment-emergent SAEs regardless of relationship and related to IMP during PAP, by primary SOC and PT.
- Listing of treatment-emergent SAEs.

Analysis of TEAE(s) leading to treatment discontinuation in PAP

- TEAEs leading to permanent treatment discontinuation during PAP, by primary SOC and PT.
- TEAEs leading to permanent treatment discontinuation during PAP presented by PT, sorted by decreasing incidence of PT in the avalglucosidase alfa arm.
- Listing of TEAEs leading to permanent treatment discontinuation during PAP, including details on dose, severity, and relationship, etc.

Analysis of adverse events with AESIs in PAP

- Treatment-emergent AESIs during PAP, by primary SOC and PT, showing the n and % of patients, sorted by decreasing incidence of PT within the avalglucosidase alfa arm.
- Treatment-emergent protocol-defined IARs during PAP, by primary SOC and PT, presented by overall n and %, as well as by start time of IAR in relation to end of infusion time (during infusion, ≤ 2 hours, >2 to 24 hours, >24 to 72 hours, >72 hours).
- Treatment-emergent algorithm-defined IARs during PAP, by primary SOC and PT, presented by overall n and %, as well as by start time of IAR in relation to end of infusion time (during infusion, ≤ 2 hours, >2 to 24 hours, >24 to 72 hours, >72 hours).
- Treatment-emergent protocol-defined IARs during PAP, by PT and maximal severity, presented by overall n and %, as well as by start time of IAR in relation to end of infusion time (during infusion, ≤ 2 hours, >2 to 24 hours, >24 to 72 hours, >72 hours).
- Treatment-emergent algorithm-defined IARs during PAP, by PT and maximal severity, showing presented by overall n and %, as well as by start time of IAR in relation to end of infusion time (during infusion, ≤ 2 hours, >2 to 24 hours, >24 to 72 hours, >72 hours).
- Listing of AESIs during PAP.
- Listing of treatment-emergent protocol-defined IARs during PAP.

- Listing of treatment-emergent algorithm-defined IARs during PAP.

Analysis of TEAEs in ETP and overall avalglucosidase alfa treatment period

Selected PAP safety analyses will be performed for ETP and/or overall avalglucosidase alfa treatment period.

In addition, a summary table of Kaplan-Meier estimates of TEAEs by 6-month time intervals will be provided for patients who only receive avalglucosidase alfa during the overall avalglucosidase alfa treatment period (no analysis if denominator < 5).

Analysis of pre-treatment and post-treatment adverse events

- All pre-treatment AEs by primary SOC and PT.
- All AEs with onset during the post-treatment epoch for PAP or ETP by primary SOC and PT.
- All post-treatment SAEs with onset during the post-treatment epoch for PAP or ETP by primary SOC and PT.
- Listing of pre-treatment AEs.
- Listing of post-treatment AEs.

Anaphylactic/hypersensitivity reactions and potential immune-mediated reactions

A comprehensive programming search of AEs which meet the Standard MedDRA Query (SMQ) (Broad + Narrow combined and Narrow alone) criteria for hypersensitivity and anaphylactic reaction will be used to identify AEs that potentially are associated with symptoms of anaphylactic and hypersensitivity reaction. Results of this search will be provided in summary tables and in a by patient listing by group. The most recent version of MedDRA SMQ will be used at the time of analysis. A medical review of these cases will be performed.

A listing of potential immune mediated reactions will be provided. Search criteria will include but not be limited to the MedDRA PTs of glomerulonephritis, nephrotic syndrome, proteinuria, haematuria, vasculitis SMQ, serositis, myocarditis, severe cutaneous adverse reactions SMQ, skin lesion, skin necrosis, arthralgia, arthritis, myalgia, arthropathy, lymphadenopathy, serum sickness, type III immune complex mediated reaction and Influenza like illness. A medical review of these cases will be performed.

